6.4 Efficacy Assessments

The pre- and then post-contrast ultrasound imaging will be evaluated for each patient as follows: grayscale, grayscale and PDI (baseline), and grayscale and SHI. While this may introduced some bias from pre- to post-contrast results, we considered this the more realistic approach to how CEUS may be used in clinical practice. Each case will be read independently by the 2 experienced co-investigators (15+ years of expertise in CEUS imaging) blinded to the surgical results and contrast-enhanced MRI evaluations, to allow repeatability to be assessed. All ultrasound studies will be rated on a quasi-continuous scale from 0 to 100 ranging from “no lesion seen (no findings)” over “definitely benign,” “indeterminate” to “definitely malignant.” Using a quasi-continuous 100-point rating scale has an intuitive probabilistic interpretation and is known to improve the assessment of the capabilities of the imaging modes studied [Wagner et al. 2001]. The SHI clips will be processed to produce CMI-SHI images [Dave & Forsberg 2009; Dave et al 2010], which will also be read by the blinded readers. Finally, sensitivity, specificity and accuracy will be calculated for all imaging modalities (baseline and SHI as well as MRI) and compared to the RMI values used to select patients for surgery [Ferrazzi et al. 1997; 2005; Moolthiya & Yuenyao 2009].

Off-line SHI TICs will be created on a pixel by pixel basis. Parametric images will be generated showing time-to-peak, perfusion rate, peak intensity (calculated in dB as the ratio of the peak to the baseline values) and area under the curve (AUC) in the area of greatest vascularity as well as parameters across the mass (based on the data from second infusion) [Eisenbrey et al. 2011b]. The TIC parameters will be compared to the lesion characterization of the other imaging modalities with pathology as the reference standard. It is our hypothesis that these new SHI based biomarkers will improve our capabilities to characterize ovarian cancers. Results will also be compared to MRI enhancement kinetics and imaging assessments obtained as part of the subjects’ standard of care.

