7.2 Statistical Analyses

7.2.1 Hypotheses

H₁: EV SHI will significantly differentiate malignant from benign adnexal masses using surgical pathology as the reference standard. As an initial end-point we speculate that an area under the ROC curve of 0.75 or better will be achieved by EV SHI.

H₂: EV SHI biomarkers will improve the characterization of benign and malignant adnexal masses compared to standard ultrasound or contrast enhanced MRI or other clinical parameters. As an initial end-point we speculate that an area under the ROC curve of 0.75 or better will be achieved by EV SHI, which will be better than low-end estimates of the accuracy of standard ultrasound, contrast enhanced MRI and other clinical parameters (which is on the order of 0.70 to 0.72).

H₃: A correlation coefficient of 0.70 will be achieved between *in vivo* SHI ovarian neovascularity measurements and iMVD.

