7.2.2 Analysis of Results

The findings of SHI will be correlated to vascular morphology (i.e., tumor angiogenesis ascertained with CD31) and other imaging and pathological findings; including size, vascularity, presence or absence of receptors and RMI values. The techniques will be compared using an analysis of variance (ANOVA) with method (i.e., baseline ultrasound imaging, SHI, or MRI) as the dependent variable and outcome as the independent variables. For the pre and post-contrast enhanced comparisons, dichotomous parameters (e.g., benign/malignant) and ranked data (less, iso, or more intense) will be analyzed with the McNemar test. The ability of the imaging tests to distinguish benign from malignant masses will be compared using ROC analysis, while the incremental validity of imaging diagnosis and morphological characteristics as well as serum biomarkers (i.e., RMI) will be analyzed using logistic regression and ROC analyses [DeLong et al. 1988; Metz 1986; Wagner et al. 2001]. Differences between ROC curves will be tested by computing Mann-Whitney statistics. All of the statistical analyses proposed for this human clinical trial will be repeated split by racial and ethnic groups to determine if clinically important race/ethnicity differences exist in the ability of SHI to characterize adnexal masses (although the limited sample size of this pilot study makes it unlikely that such differences – if any exist - will be detectable).

All analyses and computations will be performed using NCSS/PASS 2008 and Stata 12.0 (Stata Corporation, College Station, TX), while the study database will be designed and implemented in REDCap (Vanderbilt University, Nashville, TN). This database will contain all patient information (except names and other identifiers), including pathology, MRI and SHI measurements as well as other clinical variables.

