7.2.3 Sample Size Considerations

As this project involves a pilot study of a new ultrasound imaging mode (i.e., SHI) in a completely new application, no power analysis can be performed *a priori*. As a pilot study this project is not powered to

provide definitive answers to the hypotheses presented above (cf., section 7.2.1), but rather is a first step towards establishing feasibility and to provide data for a future more exhaustive study. The planned sample size of 45 subjects will provide important information on the precision of the anticipated correlation coefficient of 0.70 between in vivo SHI ovarian neovascularity measurements and iMVD such that the 95% confidence interval would be (0.51, 0.82).

The Gynecological Oncology Division at TJU evaluate more than 500 women with adnexal masses each year out of which around 1 woman/week will require surgical intervention based on their morphological characteristics (on standard imaging), CA125 levels and menopausal status [Ferrazzi et al. 1997; 2005; Moolthiya & Yuenyao 2009]. The patient population of this project will reflect the population demographics found at major American urban academic health centers. The overall hospital demographics for TJU include 60 % Caucasian, 16 % African American, 13 % Hispanic, 5 % Asian, 1 % Other, and 5 % unknown patients. We anticipate enrolling approximately 45 subjects scheduled for surgery in this project (with some 15-20 % expected to be cancers), which means we are aiming for a recruitment rate of approximately 58% (45/78).

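### The pre- versus post-contrast McNemar test in 7.2.2 is set on the benign/malignant call itself, so it tests whether the share called malignant changes, not whether more calls agree with pathology

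*Combined protocol and SAP*

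**What the plan says.** Section 7.2.2 opens the relevant sentence with "For the pre and post-contrast enhanced comparisons" and then states that "dichotomous parameters (e.g., benign/malignant) and ranked data (less, iso, or more intense) will be analyzed with the McNemar test". The benign/malignant label is the plan's own example of the paired variable. The sentence does not recode calls as right or wrong, does not split by pathology and does not mention a reference standard.

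Other parts of the plan do bring in the truth. H1 in 7.2.1 reads "EV SHI will significantly differentiate malignant from benign adnexal masses using surgical pathology as the reference standard". Section 6.4 promises that "sensitivity, specificity and accuracy will be calculated for all imaging modalities (baseline and SHI as well as MRI" will be calculated, but names no paired test for them. The next sentence of 7.2.2 says "The ability of the imaging tests to distinguish benign from malignant masses will be compared using ROC analysis".

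On the reads themselves, 6.4 says "All ultrasound studies will be rated on a quasi-continuous scale from 0 to 100", by two independent readers. It gives no value at which a rating becomes a malignant call, and no rule for using the two readers in a dichotomous comparison.

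**The concern.** McNemar's test on a paired binary variable compares its two marginal proportions. If the variable is the call, the null hypothesis is that the probability of calling a mass malignant is the same before and after contrast. That is a question about reader behaviour. H1 and H2 ask about agreement with the truth.

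Two kinds of error follow. If SHI rescues missed cancers (benign to malignant) and removes false alarms (malignant to benign), the two improvements sit in opposite discordant cells and cancel. If readers merely become readier to call malignancy once they see contrast, one cell fills and the p-value is small, although discrimination has not changed. The second case is realistic here. The post-contrast read follows the pre-contrast read, 6.4 concedes that this order may introduce some bias, and no cut-point is fixed.

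At stake is what the pilot passes on to the larger study. A p-value from this test could be reported as evidence for or against SHI when it measures neither.

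**Working it through.** **The plan's own figure.** The plan states no number for the McNemar analysis. Its only precision figure is the interval for a correlation of 0.70 with 45 subjects. Fisher's z gives atanh(0.70) = 0.867, and 1.96/√42 = 0.302. Back-transforming 0.565 and 1.170 gives (0.51, 0.82), as 7.2.3 states. This reproduces, but it has no bearing on the present point.

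**Inputs.** From 7.2.3: "We anticipate enrolling approximately 45 subjects scheduled for surgery in this project", "with some 15-20 % expected to be cancers". 0.15 × 45 = 6.75 and 0.20 × 45 = 9, so about 7 to 9 malignant and 36 to 38 benign masses. I use 8 and 37 below. The discordant counts are assumptions chosen to show the mechanism.

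**Formula.** Exact two-sided McNemar with discordant counts b and c: p = min{1, 2 × P[X ≥ max(b, c)]}, X ~ Binomial(b + c, ½).

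| Assumed change after contrast | Test on the call | Test on correct/incorrect |
|---|---|---|
| 3 missed cancers and 3 false alarms corrected | 3 v 3, p = 1.00 | 6 gained v 0 lost, p = 0.031 |
| 8 benign masses newly called malignant | 8 v 0, p = 0.008 | 0 gained v 8 lost, p = 0.008 |
| 4 cancers and 4 benign masses moved to malignant | 8 v 0, p = 0.008 | 4 gained v 4 lost, p = 1.00 |
| 3 cancers newly missed and 3 false alarms added | 3 v 3, p = 1.00 | 0 gained v 6 lost, p = 0.031 |

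In row 2 specificity falls by 8/37 = 22 points. The call test is significant, but nothing in it shows that the change is harmful. Rows 1 and 4 give the same p = 1.00 for a clear gain and a clear loss.

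**Smallest p-values.** For one-way changes p = 2 × (½)ⁿ: 5 v 0 gives 0.0625 and 6 v 0 gives 0.031. So at least 6 changes, all in one direction, are needed for p < 0.05. Among 7 to 9 cancers that means most of them must change.

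**Simulation.** Paired binormal ratings, 8 cancers and 37 benign masses, exact tests at 0.05. The operating points and correlations are assumptions, except that the last row takes its ROC areas from H2. Entries are approximate shares of trials with p < 0.05.

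| Scenario | Call | Pooled correctness | Within cancers | Within benign |
|---|---|---|---|---|
| (a) ROC area 0.75 at both reads, correlation 0.6, specificity 80% to 60% by threshold shift | 65% | 24% | below 1% | 52% |
| (b) Sensitivity 53% to 85%, specificity 75% to 90%, correlation 0.5 | 7% | 60% | 2 to 3% | 34 to 35% |
| (c) ROC area 0.70 or 0.72 to 0.75, correlation 0.5, specificity 75% at both reads | 3% | 3% | below 1% | 2% |

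Under the same binormal model, scenario (b) corresponds to ROC areas of Φ[(Φ⁻¹(0.53) + Φ⁻¹(0.75))/√2] = 0.70 and Φ[(Φ⁻¹(0.85) + Φ⁻¹(0.90))/√2] = 0.95. That is a far larger gain than the plan speculates in H2.

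**The case against.** The strongest reply is that accuracy is tested elsewhere. H1 and H2 are both framed on the area under the ROC curve, and 7.2.2 plans ROC comparisons, a test of differences between curves and logistic regression for incremental value. This stands. A reader might infer from the McNemar sentence that the plan has no valid test of whether characterization improves; the documents do not support that. What the ROC analysis does not do is test the dichotomous measures listed in 6.4. The analysis of variance also named in 7.2.2 does not fill the gap, because it is not a paired test of those proportions.

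Second, the sentence is broad and partly descriptive. It also covers imaging features, for which asking whether the read changed is legitimate, and the authors may have meant agreement with pathology. That is possible, but the benign/malignant label is the example they give, and an analyst following the text would test the calls.

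Third, the numbers can be made to say too much. The 60% in scenario (b) belongs to pooled correctness, not to the stratified tests recommended below, and it assumes a gain well beyond the plan's. At the plan's own gain, scenario (c), neither the call test nor the correctness test rejects more than about 3% of the time. Stratified tests also still respond to a threshold shift: in scenario (a) the test in benign masses rejects in about 52% of trials. All of this stands.

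Fourth, this is a pilot that disclaims definitive answers. That lowers the consequence but does not make the test answer its question.

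**Conclusion.** The point holds, at moderate severity. Read as written, the McNemar analysis of the benign/malignant call tests for a change, in either direction, in the proportion called malignant. It can give p = 1.00 when six calls are corrected and none lost, and p = 0.008 when eight become wrong. The cancellation is algebraic and depends on no assumption about reader performance; only the simulated percentages do.

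The scope is narrow. H1 and H2 keep their ROC route against pathology. The loss is that the paired sensitivity, specificity and accuracy of 6.4 have no suitable test.

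Two stronger readings should be resisted. One is that the test looks only for more malignant calls; it is not restricted to that direction. The other is that rewording would give the pilot useful power; with 7 to 9 cancers it would not. The repair corrects the question that is asked, not the precision of the answer.

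**What to change.** In 7.2.2:

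- Keep McNemar on raw reads only for descriptive imaging features, where the question is whether the read changed.
- For the benign/malignant call, prespecify a cut-point on the 0-100 scale and analyse each reader separately.
- Compare pre- and post-contrast calls against surgical pathology within malignant masses (sensitivity) and within benign masses (specificity).
- Report the paired difference with its confidence interval as the main result for each, and exact McNemar as supportive.
- State that the ROC comparison remains primary, because the stratified tests still react to a threshold shift and the sensitivity test needs at least 6 one-way changes among 7 to 9 cancers.

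Cost: a few sentences of SAP text, with no new data collected. The cut-point should be fixed before reads are compared with pathology. The downside is that the small-sample intervals will be wide, particularly for sensitivity.

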1.1 Background

Among the early changes that differentiate normal from cancerous tissues is the process by which the tumor develops its blood supply, tumor angiogenesis [Folkman 1990; Li 2000]. In addition, angiogenic vascular morphology, often quantified as the intra-tumoral microvessel density (iMVD), is an independent predictor of malignant disease; including in the ovaries [Brawer et al. 1992; Labiche et al. 2009; Palmer et al. 2007; Weidner et al. 1991; Weind et al. 1998; Wang et al. 2011]. Angiogenesis is a prerequisite for tumor growth greater than 2 mm³ and is also a key factor of metastasis by allowing the ingrowth of vessels into a tumor providing a pathway for systemic dissemination via the blood or lymph system [Holmgren et al. 1995; O'Reilly et al. 1994]. Therefore, tumor angiogenesis is an important marker for imaging adnexal masses. The opportunity for noninvasive imaging of tumor angiogenesis is strengthened by the fact that vessels

form a substantial portion of the mass of malignant tumors, contributing up to 10 % of the total volume of the tumor [Jain 1994]. Currently adnexal masses are imaged with standard EV US, with contrast enhanced MRI or computed tomography (CT) as well as, more rarely, with positron emission tomography (PET) [Bazot et al. 2008; Fleischer et al. 2012; Mohaghegh & Rockall 2012; Moyle et al. 2010]. While overall accuracies of 88 to 93 % have been reported for the latter modalities [Bazot et al. 2008; Mohaghegh & Rockall 2012], they are quite expensive and employ contrast agents which can produce marked adverse reactions, while CT also exposes patients to significant radiation.

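### With 7 to 9 cancers expected, section 7.2.2 should fix the coding, size and estimator of its logistic models: ordinary maximum likelihood inflates the effects and may give no finite odds ratio for a binary MRI call

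*Combined protocol and SAP*

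**What the plan says.** Section 7.2.2 states that the "incremental validity of imaging diagnosis and morphological characteristics as well as serum biomarkers (i.e., RMI) will be analyzed using logistic regression", together with ROC analyses. It does not say how the imaging diagnosis is coded, how many terms share a model, which estimator or test is used, or what happens if the fit has no finite solution.

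The same section does refer to a two-way call, but in a different sentence and for a different test: "dichotomous parameters (e.g., benign/malignant) and ranked data (less, iso, or more intense) will be analyzed with the McNemar test". Section 6.4 gives ultrasound a graded scale: "All ultrasound studies will be rated on a quasi-continuous scale from 0 to 100". MRI comes from standard care, and no comparable rating is described for it.

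On numbers, section 7.2.3 anticipates about 45 subjects, "with some 15-20 % expected to be cancers". On performance, section 7.2.1 speculates that SHI will reach an AUC of at least 0.75, against low-end accuracy for standard ultrasound, MRI and clinical parameters "which is on the order of 0.70 to 0.72". Section 1.1 says that "overall accuracies of 88 to 93 % have been reported for the latter modalities", meaning MRI, CT and PET taken together.

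**The concern.** The gain from SHI over RMI, baseline ultrasound or MRI is the result closest to the primary objective, and it is meant to feed a larger study. Two things can go wrong when ordinary logistic regression meets 7 to 9 events.

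First, maximum-likelihood coefficients are biased away from zero in small samples. This happens even when every fit converges, so the pilot would pass on an exaggerated SHI effect.

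Second, if a two-way call is positive in every cancer, the table of call by pathology has an empty cell and the fitted odds ratio is infinite (separation). Women negative on that call then tell the fit nothing about the other predictors. A sensitive test is the most likely to trigger this. With no remedy written down, one would be chosen after seeing the data.

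**Working it through.** **The plan's own figures.** Section 7.2.3 says: "The planned sample size of 45 subjects will provide important information on the precision of the anticipated correlation coefficient of 0.70". Fisher's z gives tanh(atanh(0.70) ± 1.96/√42) = (0.512, 0.824), which matches the stated (0.51, 0.82). This is the plan's only precision figure, and it does not concern the logistic models.

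**Events.** 0.15 × 45 = 6.75 and 0.20 × 45 = 9, so 7 to 9 cancers and 36 to 38 benign masses.

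**Bias and test size without separation.** Data sets of 45 women with 7 or 9 cancers were simulated with continuous predictors at the plan's AUCs.
- With two or three predictors, the mean maximum-likelihood coefficient was 18 to 27% too large, and the nominal 5% likelihood-ratio test rejected a true null in 6.4 to 7.0% of data sets. Firth estimates were within about 2% of the truth.
- A second set of runs, with three to four predictors (AUCs 0.70 to 0.75, correlation 0.3), gave 26 to 42% and 6.5 to 7.6%. Firth gave a 0 to 4% excess and a test size of 4.0 to 4.8%. The problem grows with the number of terms.

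**Chance that one binary call misses no cancer.** This is sensitivity raised to the number of cancers. The documents give accuracies only, so the sensitivities are assumptions:

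| Assumed sensitivity | 7 cancers | 9 cancers |
|---|---|---|
| 0.72 | 10% | 5% |
| 0.88 | 41% | 32% |
| 0.93 | 60% | 52% |

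**Separation in whole models** (simulated, detected by linear programming):
- RMI, an SHI rating and one binary MRI call: about 6 to 12% at MRI sensitivity and specificity of 0.72, and about 35 to 65% at 0.88 to 0.93.
- SHI rating plus the MRI call alone: 9% and 6% (7 and 9 cancers) at 0.72, 42% and 32% at 0.88, 64% and 57% at 0.93. Cutting terms does not by itself protect the MRI comparison.
- Continuous ratings at AUC 0.75: 0 to 0.1% for SHI plus RMI, and 0.5 to 2.3% with baseline ultrasound and MRI also entered as ratings. If ratings reached AUC 0.90, this would be 1 to 2% for one rating plus RMI but 29 to 39% for three plus RMI.

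**What fails and what survives.** Suppose a call is positive in 7 of 7 cancers and 8 of 38 benign masses.
- The ordinary odds ratio is infinite. Software reports a Wald p of about 1.0, against a Fisher exact p of 0.00014.
- The likelihood-ratio chi-square is 2 × {[7 ln(7/15) + 8 ln(8/15)] − [7 ln(7/45) + 38 ln(38/45)]} = 2 × (−10.36 + 19.45) = 18.2, p = 0.00002.
- The AUC of the call is (1 + 30/38)/2 = 0.895.
- The Firth odds ratio is (7.5 × 30.5)/(8.5 × 0.5) = 53.8.

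**Information left for SHI if MRI misses no cancer.** Only MRI-positive women count. At an assumed specificity of 0.90 that is 7 + 3.8 to 9 + 3.6, about 11 to 13 women. At 0.72 it is 7 + 10.6 to 9 + 10.1, about 18 to 19.

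**The case against.** A reader might infer that the incremental-value analysis will often have no solution, and that it collapses precisely when a test finds every cancer. The documents do not support that, for four reasons.

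- The plan never says that two-way calls enter the logistic model. The benign/malignant wording belongs to the McNemar sentence, and ultrasound has a 0-100 rating with which separation is rare.
- How often separation occurs depends on sensitivities that the documents do not give. The 88 to 93% figures are accuracies pooled over several modalities. At the low-end 0.72 of section 7.2.1, an MRI call separates the model in only about 6 to 12% of data sets.
- The plan names no Wald test, and it pairs the regression with ROC analysis. The likelihood-ratio test and the AUC stay finite, so only part of the output is lost.
- A call that misses no cancer is not the only route: one with no false positives, or a combination of predictors, can also separate the data.

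It is also fair to say that section 7.2.3 disclaims definitive answers, that a test size of 6.5 to 7% matters little in a pilot, and that exact or ordinary likelihood-ratio methods are alternatives to Firth.

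All of this stands and limits the size of the point. It does not remove the event count, the missing specification, the average inflation or the exposure of MRI, which is a named comparator in the primary objective. Pilot status excuses low power. It does not excuse passing on an inflated or infinite odds ratio.

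**Conclusion.** The point holds as a cheap improvement, of minor to moderate weight. On the plan's own 7 to 9 cancers, ordinary maximum likelihood would overstate coefficients by about 18 to 27% on average with two or three continuous predictors, and by more with further terms. Its likelihood-ratio test would be slightly liberal. These figures rest on simulation at the plan's speculated AUCs.

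The separation risk is conditional. It is about 0 to 2% with ratings at AUC 0.75. For a binary MRI call it runs from about 6 to 12% up to 35 to 65%, depending on whether assumed sensitivity and specificity lie at 0.72 or at 0.88 to 0.93. When it occurs, the odds ratio, Wald test and Wald interval are lost, but not the whole analysis.

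**What to change.** In section 7.2.2:
- enter the ultrasound modes as their 0-100 ratings;
- limit each incremental model to one comparator (RMI, baseline ultrasound or MRI) plus one SHI measure;
- fit by Firth penalised likelihood, with penalised likelihood-ratio tests and profile penalised-likelihood intervals in place of Wald.

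The first two steps deal with most of the separation risk for ultrasound. The third is needed for a binary MRI call and for the average inflation.

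The cost is wording and a different fitting routine, with no new patients or data. Estimates shrink slightly. Nominal power falls (20 to 27% against 29 to 33% in simulation), part of the maximum-likelihood figure being its raised error rate. Whether the packages named in section 7.2.2 offer the Firth fit was not checked, and a routine beyond the default logistic command may be needed.

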4. TRIAL POPULATION

Trial Population: This trial will consist of up to 45 adult women (21 years of age or older) at TJU, who have an adnexal mass and are scheduled for surgery based on their morphological characteristics (on standard imaging), CA125 levels and menopausal status.

Subjects eligible for trial enrollment will be identified by the co-investigator, [name], from his patient population of subjects scheduled for surgery of an adnexal mass. The research coordinator for this study will explain the study to the patients. The patient will be given time to consider the risks and benefits of the study and ask questions about participation. The coordinator will review the consent form with the woman and then the patient will be given the form to review. The patient, coordinator, and a study investigator will all sign the consent form. The patient will be given a copy of the signed consent form for

their records.

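### For the added value of SHI over RMI, Section 7.2.2 should test the SHI term in the logistic model; the only ROC-difference test it names is severely conservative for nested fitted models

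*Combined protocol and SAP*

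**What the plan says.** Section 7.2.2 gives ROC methods two jobs in one sentence. The imaging tests are to be compared with each other by ROC analysis. Then the incremental validity of imaging, morphology and "serum biomarkers (i.e., RMI) will be analyzed using logistic regression and ROC analyses", with the DeLong paper among the references closing that sentence. The next sentence reads "Differences between ROC curves will be tested by computing Mann-Whitney statistics". No other test is named for either job. The plan does not write out a base model or an extended model, does not mention a Wald or likelihood-ratio test of an added term, and does not rule one out.

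Section 7.2.1 supplies the expected performance: "an area under the ROC curve of 0.75 or better will be achieved by EV SHI", against comparators whose accuracy "which is on the order of 0.70 to 0.72". Section 7.2.3 gives the size: "We anticipate enrolling approximately 45 subjects scheduled for surgery in this project", "with some 15-20 % expected to be cancers". It also says the pilot is not powered for definitive answers.

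**The concern.** Incremental validity by logistic regression ordinarily means fitting a model without the new marker and one with it to the same patients, then asking whether the second does better. If that question is answered by comparing the two models' ROC curves, the sentence that follows supplies the DeLong test.

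DeLong's reference distribution is derived for two scores fixed in advance. Here the larger model contains the smaller and both sets of coefficients are estimated from the data being scored. If SHI adds nothing, its coefficient is near zero and the two fitted scores rank the women almost identically. The AUC difference and its estimated standard error then both shrink towards zero, and their ratio does not behave as a standard normal.

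At stake is the pilot's message on whether SHI adds to what RMI already tells the surgeon. A real gain would usually appear as a non-significant AUC difference, and these results are meant to shape the next study.

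**Working it through.** **The plan's own figure.** The plan gives no precision or power figure for the ROC or incremental analysis. Its only precision figure is the interval for a correlation of 0.70 with 45 subjects. Fisher's z reproduces it: tanh(atanh(0.70) ± 1.96/√42) = tanh(0.867 ± 0.302) = (0.512, 0.824), printed as (0.51, 0.82).

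**Inputs from the documents.** N = 45. Cancers: 0.15 × 45 = 6.75 to 0.20 × 45 = 9, so 7 to 9. SHI AUC 0.75. Comparator 0.70-0.72, called accuracy in Section 7.2.1 and read here as AUC.

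**Assumptions not in the documents.** Binormal markers; RMI as the sole base covariate; within-class RMI-SHI correlation ρ of 0 or 0.3; two-sided 0.05.

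**Set-up.** An AUC of A corresponds to a mean shift d = √2·Φ⁻¹(A): 0.742 for 0.70, 0.824 for 0.72 and 0.954 for 0.75. Under the null (SHI adds nothing given RMI) the SHI shift is ρ × d of RMI. In each simulated trial, logistic models with RMI only and with RMI + SHI are fitted to the same 45 women. The tests are:
- DeLong: z = (AUC₂ − AUC₁)/√(S₁₀/m + S₀₁/n), where m and n are the numbers of cancers and benign masses, and S₁₀ and S₀₁ are the variances of the paired differences in placement values.
- Likelihood ratio (LR): 2(ℓ₂ − ℓ₁) against 3.84. The Firth version replaces ℓ by ℓ + ½ log|I(β)|.
- Wald test of the SHI coefficient.

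There were 3,000 replicates per setting at N = 45, and 1,000 at larger N.

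**Size of the true gain.** With base AUC 0.72 and SHI AUC 0.75, the best combination has AUC Φ(D/√2), where D² = (d₁² − 2ρd₁d₂ + d₂²)/(1 − ρ²).
- ρ = 0: D² = 0.679 + 0.910 = 1.589, AUC 0.81.
- ρ = 0.3: D² = (1.589 − 0.472)/0.91 = 1.228, AUC 0.78.

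So a true gain of about 0.09 or 0.06 is there to be found.

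**Null rejection rates** (nominal 5%; base AUC 0.72 or 0.85 at N = 45 and N = 450; ρ 0 or 0.3):

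| Setting | DeLong on nested fits | LR | Wald |
|---|---|---|---|
| N = 45, 7-9 cancers | 0.1-0.6% | 5.9-7.4% | 2.6-4.1% |
| N = 450, 80 cancers | 0.0-0.4% | 4.3-5.2% | 4.1-5.0% |

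**Control.** DeLong applied to two raw, unfitted markers of equal AUC (N = 45, 8 cancers) rejects in 6.4%. The fault is confined to nested fitted models.

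**Power at the plan's AUCs, N = 45:**

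| ρ | Cancers | DeLong, base 0.70 | DeLong, base 0.72 | LR, base 0.72 | LR recalibrated to 5%, base 0.72 |
|---|---|---|---|---|---|
| 0 | 7 | 14% | 13% | 60% | 58% |
| 0 | 8 | 15% | 14% | 63% | 59% |
| 0 | 9 | 17% | 15% | 67% | 63% |
| 0.3 | 7 | 8% | 7% | 41% | 35% |
| 0.3 | 8 | 10% | 8% | 46% | 40% |
| 0.3 | 9 | 9% | 8% | 49% | 43% |

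The plain LR test is slightly liberal here. A separate simulation with 8 cancers and base AUC 0.72 used the Firth version: size 4-5%, power about 60% (ρ = 0) and 38% (ρ = 0.3), against 15% and 7% for DeLong. The advantage is therefore not bought with false positives.

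**Sensitivity.** With an assumed SHI AUC of 0.85 (base 0.72), DeLong has 26-46% and LR 83-95%. At N = 260 with 45 cancers (0.72 v 0.75, ρ = 0.3) it is 59% against 99%, so a follow-on study that copied the method would still pay for it.

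**The case against.** The strongest reply is that the plan never commits to this. A reader might infer that Section 7.2.2 prescribes DeLong on nested models; it does not say so. No nested pair is written out, and RMI is listed among the items whose incremental validity is examined, not named as the base. Logistic regression is named first and could itself supply a valid test of the added term. The Mann-Whitney sentence fits the head-to-head comparison of imaging tests equally well, and there it is appropriate. All of this stands. What remains is that the plan names no other test for the increment, so the analyst is left with the conservative one or an unplanned choice.

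Second, a reader might take this for the trial's central question. The documents do not support that: H1 to H3 concern SHI's own AUC, its AUC beside that of the comparators, and a correlation with iMVD. Section 6.4 also sets RMI beside the modalities through sensitivity, specificity and accuracy. Incremental validity is half a sentence in Section 7.2.2.

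Third, the better test is no cure for 45 women. At ρ = 0.3 the Firth test still misses about 62% of real gains (100 − 38). That is true, and Section 7.2.3 disclaims definitive answers. Even so, 38% is more than five times 7% from the same data.

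Finally, a reader might infer that entering morphology beside RMI counts the same information twice. Section 4 describes women "scheduled for surgery based on their morphological characteristics (on standard imaging), CA125 levels and menopausal status", and Section 6.4 says RMI was used for that selection, so overlap is a fair inference. But Section 7.2.2 does not put both in one model, and logistic covariates are mutually adjusted. What is left is loose wording: RMI is called a serum biomarker when it appears to be a composite index.

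**Conclusion.** The point holds as a gap in specification whose natural filling is a poor test. If the increment is judged by DeLong on nested fitted models, the test runs at about 0.1-0.6% instead of 5%. At the plan's own AUCs and cancer counts it has 13-17% power (ρ = 0) or 7-10% (ρ = 0.3), roughly a fifth to a quarter of what a test of the SHI term has. The word invalid could suggest inflated false positives; the error runs the other way, towards missed benefit.

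The sizes rest on the assumptions listed in the working, chiefly the correlation, which the documents do not give. In every setting tried DeLong had well under the power of the test of the term. Priority is moderate: a secondary analysis, in a pilot that claims no power, whose results are intended to inform a larger study.

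**What to change.** In Section 7.2.2:

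- State the base model and the extended model. Keep the base small, because 7-9 cancers over two predictors give only 3.5-4.5 events per coefficient. Log RMI alone is one reasonable choice, not the only one.
- Test incremental value by a Firth-penalized likelihood-ratio test of the SHI term, and state the significance level and sidedness.
- Report the change in AUC as an estimate, preferably optimism-corrected with a bootstrap interval, without a DeLong p-value.
- Keep the Mann-Whitney/DeLong test for head-to-head comparison of separate, unfitted modality ratings (SHI, baseline ultrasound, MRI), and say that this is its scope.
- As a wording correction only, call RMI a composite index; if a serum term is meant, name CA125.

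The cost is a few sentences and a routine penalized fit, with no new patients or measurements. The downside is that the increment is tested on the odds scale, so the p-value does not refer directly to the AUC change that readers will look at.
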